1	Protocol							
2	Executive summary							
3 4	Title: Circular pOlyethylene drape in preVEntion of suRgical site infection (COVER trial): study protocol for a randomized controlled trial							
5 6	Investigational product: O Trac, Asung Medical (a double-ring type of sterile, cylindrical wound protector consisting of inner and outer rings with a polyethylene sheath)							
7	Protocol number: NCT#03170843							
8 9	Study desig	n: A prospective, multicenter, patient-blinded, randomized controlled trial with two parallel arms.						
10	Number of s	ites: Up to 13 sites of secondary or tertiary hospitals in South Korea						
11 12	Number of subjects: A total of 458 patients undergoing open laparotomy, either elective or emergent, for gastrointestinal tract surgery							
13 14	Study population : Male and female patients between the ages of 18 and 75 years requiring gastrointestinal surgery.							
15	Study Criter	ria:						
16	Inc	clusion criteria						
17	1)	Between the ages of 18 and 75 years						
18	2)	Undergoing elective or emergent open abdominal surgery						
19	3)	Undergoing surgery on the stomach, small intestine or colon and rectum						
20	Exclusion criteria							
21	1)	Presence of concurrent infection in the abdominal wall						
22	2)	Open conversion from laparoscopic surgery						
23 24	3)	Presence of poor nutritional status indicated by a nutrition risk screening (NRS) 2002 score greater than 3						
25	4)	Undergoing combined hepatobiliopancreatic surgery						
26	5)	Pregnancy or breast feeding						
27 28 29 30	6)	Moderate to severe immunosuppression state (defined as previous organ or bone marrow transplantation, concurrent steroid administration of more than 10mg prednisolone daily or an equivalent dose of any other steroid, concurrent administration of other immunosuppressive or chemotherapeutic agents within the last 2 weeks prior to trial intervention)						

45

- 32 Interventions: The incision site was covered by a circular polyethylene drape in the experimental group and the 33 conventional surgical dressing gauze in the control group during the surgery
- 34 Study objective: To determine whether the device helps to reduce the overall rate of surgical site infection, SSI.

35 **Study Endpoints:**

- 36 Primary outcome
- 37 The rate of SSI, defined by the diagnostic criteria suggested by the Centers for Disease Control 38 (CDC), within 30 days after surgery
- 39 Secondary outcome
- 40 The length of postoperative hospital study
- 41 The incidence of 30-day postoperative complications stratified according to the modified Clavien-42 Dindo classification

43 Clinical visit and assessment schedule

44 Baseline at the enrollment, postoperative day 0, postoperative day 1-2, postoperative week 1, postoperative week 2-3, postoperative week 4

			Study period						
		Enrollment	Allocation	Post-allocation	Close-out				
	Time point	-2 to 0 day	Operation day (day 0)	Postoperative day 2	Postoperative Week 1	Postoperative Week 2-3	Postoperative Week 4-5	Postoperative week 4-5	
Enrollment	Eligibility screen	х							
	Informed consent	х							
	Randomization		Х						
	Allocation		X						
Intervention	Experimental intervention		x						
	Control intervention		х						
Assessment	Demographical x data								
	Medical history	Х							
	Nutritional status	х							
	Laboratory	X	X	X					

examination					
Parameters of					
surgical	X				
procedure					
Body					
temperature	X				
Documentation		X	X	X	
of SSI		Λ	Λ	Λ	
Documentation					
of other		X	X	X	
complication					
Length of					v
hospital stay					Х
Readmission					v
rate					Х

Original protocol

1. Objectives

The COVER trial aims to investigate the effect of a dual-ring, plastic wound protector in open abdominal surgery. It is designed to test whether the device helps to reduce the overall rate of SSI development within 30 days postoperatively by 40% compared with that of the control group. In particular, the COVER trial includes patients who are undergoing an open abdominal surgery for contaminated or dirty/infected wounds, as well as those undergoing an open abdominal surgery for clean or clean-contaminated wounds, which allows a thorough investigation of the wound protector's effects, depending on the degree of contamination.

2. Background and rationale

Surgical site infection (SSI) is a common postoperative complication that is associated with considerable morbidity and mortality. [1-3] The rate of SSI is estimated to range from approximately 10% to 30% after elective abdominal surgery, depending on the presence of risk factors, type of procedure and degree of endogenous contaminants. [1,4,5] In cases of fecal peritonitis, the SSI rate may reach up to 35~40%. [6,7] Despite organizational, systematic approaches for preventing SSI based on evidence, such as preoperative antibiotic prophylaxis and antiseptic skin cleansing, SSI is still a major problem associated with increased hospital cost, prolonged hospital stays and unsatisfactory quality of life. [8]

The risk of developing an SSI will increase when the surgical incision site is exposed to large amounts of virulent bacteria in a contaminated surgical field. [9] The risk has led to the idea of developing a physical barrier for the wound edge that can hinder direct exposure of the surgical incision edges to the contaminated field. Several devices that are designed for wound edge protection and have a similar design involving a flexible plastic wound cover placed in the laparotomy site are currently on the market. Prospective studies and randomized clinical trials (RCTs) have been conducted to evaluate the effectiveness of plastic wound protectors for reducing the incidence of SSI. [8,10-13]

The largest RCT evaluating the effectiveness of wound protectors in reducing SSI is the Reduction of Surgical Site Infection using a Novel Intervention (ROSSINI) trial. [8] In this study, the drape type of wound protector was compared with standard intraoperative care. The results showed that the use of a wound edge protector during open abdominal surgery did not reduce the rate of SSI. Similarly, RCTs using a drape type of wound protector applied in colorectal surgery reported no benefit of the wound protector in reducing SSI. [10,11] However, several other studies have claimed contrasting results. The BaFO trial, with 608 patients undergoing laparotomy at 16 different medical centers in Germany, demonstrated that the patients who used wound protection drape devices experienced SSI at a lower rate than those who did not. [12] A Japanese single-center RCT with 221 patients enrolled to investigate the effect of a double ring, circular wound protector applied in non-traumatic gastrointestinal surgery also showed that the rate of SSI was significantly lower in the experimental group than in the control group. [13]

The effect of wound protectors in abdominal surgery is still controversial and remains to be elucidated.

84			ell designed, multicentered RCT evaluating the effect of the dual-ring type of wound protector in open					
85		abdominal surgery, particularly for contaminated or dirty infected wounds, has not yet been conducted.						
86	3.	Expo	erimental Plan					
87		A.	Trial type – this is a prospective, multicentered, patient-blinded, randomized controlled trial with					
88			two parallel comparison arms.					
89		B.	Trial sites –Secondary or tertiary hospitals in South Korea					
90			All participating investigators should be educated on the basis of the International Conference on					
91			Harmonization (ICH) of Technical Requirements for Registration of Pharmaceuticals for Human Use,					
92			which serves as the good clinical practice (GCP) guidelines for this trial. This trial is open for					
93			recruiting participating centers.					
94		C.	Trial population and eligibility					
95			All gastrointestinal surgical patients undergoing open abdominal surgery, either elective or emergent,					
96			will be screened for eligibility.					
97			■ Inclusion criteria					
98			(1) Between the ages of 18 and 75 years					
99			(2) Undergoing elective or emergent open abdominal surgery					
100			(3) Undergoing surgery on the stomach, small intestine or colon and rectum					
101			Exclusion criteria					
102			(1) Presence of concurrent infection in the abdominal wall					
103			(2) Open conversion from laparoscopic surgery					
104			(3) Presence of poor nutritional status indicated by a nutrition risk screening (NRS) 2002					
105			score greater than 3					
106			(4) Undergoing combined hepatobiliopancreatic surgery					
107			(5) Pregnancy or breast feeding					
108			(6) Moderate to severe immunosuppression state (defined as previous organ or bone marrow					
109			transplantation, concurrent steroid administration of more than 10mg prednisolone daily					
110			or an equivalent dose of any other steroid, concurrent administration of other					
111			immunosuppressive or chemotherapeutic agents within the last 2 weeks prior to trial					
112			intervention)					
113		D.	Recruitment and trial timeline					

Patients will be recruited for approximately 48 months. After completion of informed

114

consent, each subject will be registered. The last follow-up will be made approximately 30 days after the last recruited patient undergoes the trial intervention. An interim analysis is planned when 50% of the enrollment is reached. Depending on the results of the interim analysis, the subsequent research process and timeline can be modified.

E. Randomization and blinding

Stratification will be performed according to the participating center and the type of wound classification. The wound types will be divided into two groups: one group with clean or clean-contaminated wounds and the other group with contaminated or dirty, infected wounds. A web-based patient registry (http://cover.e-trial.co.kr) will be applied to generate the allocation sequence immediately before the beginning of the operation, providing adequate concealment for the allocation sequence. The group allocation and randomization number will be predefined by a biostatistician from the Catholic Medical Center in Seoul, South Korea. A permuted block randomization with the size of two or four will be applied. Participating investigators cannot be blinded to the allocated treatment. However, the patient will be blinded to the trial intervention since they are under general anesthesia once the operation starts. The data manager will also be blinded because there is no direct access to either the trial intervention or the randomization.

F. Screening failure

Registered subjects who are ineligible for the study based on screening assessments will be considered protocol violation due to screening failure and registered as such with reason for failure.

G. Interventions

Preoperative bowel preparation, type of skin preparation and drape, the use of perioperative antibiotics and the details of the surgical procedure will follow the policy of an individual surgeon at each center. The experimental arm will be provided with a circular polyethylene drape (O Trac, Asung Medical, South Korea) to cover the incision site in the abdomen. It is a double-ring type of sterile, cylindrical wound protector consisting of inner and outer rings with a polyethylene sheath. The wound protector is left in situ throughout the operation and is removed immediately before closing the abdominal wall. The method of wound closure and insertion of wound drainage will also follow the policy of an individual surgeon at each center. For the control arm, conventional surgical dressing gauze will be used to protect the incision site during the surgical procedure. There are no differences in surgical techniques, other devices or environments.

H. Risks to the participants

No additional risks to the participants are expected. The circular polyethylene wound protector has established clinical safety and has already been used in clinical applications with the approval of the Korean Medical Device Information and Technology Assistance Center. None of the technical details other than wound protection are affected by the trial.

I. Outcomes

150

151

152

153

154

155

156

157

158

159

160

161162

163

164

165

166

167

168

169

170

171

172

173

174

175

176

177

178

179

180

181

182

183

184

185

186

The primary end point is the rate of surgical site infection (SSI), defined by the diagnostic criteria suggested by the Centers for Disease Control (CDC), within 30 days after surgery. SSIs are classified as either superficial incisional, deep incisional or organ/space. [14] The postoperative wound condition will be evaluated at postoperative weeks 1, 2 and 4-5. The secondary end points include the length of postoperative hospital stay, the readmission rate and the rate of surgical complications other than SSI. The incidence of 30-day postoperative complications other than SSI. The incidence of 30-day postoperative according to the modified Clavien-Dindo classification. [15]

J. Data management and monitoring

A newly developed, web-based, electronic case reporting form (e-CRF) will be used to record data for the included patients. Baseline characteristics, including age, sex, body mass index, American Society of Anesthesiologists score, history of smoking and alcohol consumption, history of previous chemotherapy, radiotherapy, abdominal surgery or steroid or immunosuppressive drug use, history of diabetes or malignancies in the gastrointestinal tract and nutritional status based on the NRS 2002 score, will be collected. Laboratory parameters (white cell counts, C-reactive protein, and albumin levels) will be collected preoperatively, on the operation day and on postoperative day 2, if available. The parameters for the surgical procedures, including operation type (emergent or elective), site of operation (stomach, small bowel or large intestine), level of wound contamination according to CDC classification, method of skin preparation, antibiotic use, operation time, bowel anastomosis and stoma formation, wound closure material, length of skin incision, draining tube for the wound and body temperature during the surgical procedure, will be collected. The surgical wounds are classified as clean, clean-contaminated, contaminated, and dirty wounds, according to the magnitude of the bacterial load. [16] Postoperatively, the surgical wound will be evaluated at postoperative week 1, 2 and 4-5. A photograph of the wound will be taken at each office visit and documented in the eCRF. If SSI is detected, the classification and the postoperative date of diagnosis will be recorded. Bacterial culture of the infected wound will be performed. Postoperative complications according to the modified Clavien-Dindo classification, postoperative length of hospital stay and readmission will be noted. An investigator or research coordinator at each center will enter the data using the eCRF. At the end of the trial, the study data and personal information of the enrolled patients will be archived for 3 years. The trial data will be monitored by an independent institution (Medical Excellence) in Seoul, Korea. Monitoring will be performed in accordance with ICH-GCP guidelines. [17]

K. Safety evaluation and reporting of adverse events

All adverse events or serious adverse events, occurring from the moment of randomization until the end of the 30-day follow-up, will be recorded and reported by the investigators.

L. Statistical methods

(1) Sample size calculation

The sample size was calculated based on the primary end point of this trial. Previous reports on the incidence of SSI have indicated that the rate of SSI may vary depending on the wound classification, the procedure, the surveillance criteria and the quality of data collection. [18] The incidence of SSI for clean/clean-contaminated wounds has been reported to be as high as 10%. [19] For contaminated wounds, the incidence was approximately 25%. [7,18] For dirty, infected wounds, the incidence may reach up to 40%. [5-7] In this trial, the ratio of operations with clean/clean-contaminated, contaminated and dirty, infected wounds are assumed to be 20:40:40; therefore, the expected incidence of SSI for the control group as 28%. For the experimental group, the incidence of SSI will be decreased by 40%. Thus, the rate of SSI in the experimental group will be approximately 17%. The sample size was determined to achieve a study power of 80%, with 95% two-sided confidence limits. The actual sample size amounts to 434 participants. However, considering a dropout (lost to follow-up, retracted consent or protocol violation) rate of up to 5%, a total of 458 patients, 229 patients in each group, will be enrolled in this study.

(2) Statistical analysis

The statistical analysis will be performed by an independent statistician from the Catholic Medical Center (Seoul, South Korea). The interim and final results will be analyzed mainly for the intention-to-treat population and, additionally, for the per-protocol population. The rate of 30-day postoperative SSI will be evaluated in all patients and analyzed mainly for the intention-to-treat population and, additionally, for the per-protocol population. The rate of 30-day postoperative SSI will be evaluated in all patients and analyzed according to the wound classification (superficial incisional, deep incisional and organ/space SSIs), as defined by the CDC. Pearson's χ^2 test or Fisher's exact test will be used to analyze nominal data; Student's t-test and the Wilcoxon rank-sum test will be used for continuous data. To estimate the independent risk factors for 30-day postoperative SSI, logistic regression analysis will be performed. The statistical analysis will be conducted using SAS V.9.4 (SAS Institute)

M. Ethics, patient withdrawal, and dissemination

Written informed consent will be obtained from each study participant prior to any protocolrelated activities in accordance with ethical approval. The principal investigator, surgeon coinvestigator, or one of the approved study coordinators must explain orally and in writing the details
of the study. Enrolled patients can withdraw their participation at any time if desired. In this case, the
patients will have no disadvantages. The investigator will record any patient withdrawal in the CRF.
Decisionally-impaired and cognitively impaired persons will not be enrolled, as considered a
vulnerable population. Although staff and employees of the participating sites are considered
vulnerable populations, they may be eligible to participate in this study. If an employee is a potential
candidate for this study, the subject will be informed that participation or refusal to will would not
influence grades, employment, or subsequent recommendations. Every effort will be made to prevent

coercion at any time in the process. Students and house staff cannot be asked to participate in research conducted while under the direct supervision of the investigator; therefore, those subjects will not be enrolled.

The investigators and study coordinators are obligated to keep the anonymity and confidentiality of subjects participating in this study. Documents that can identify the subject by name will be tightly regulated to keep confidentiality, except to the extent necessary to allow monitoring and audition by internal and external regulatory authorities.

All information, including name and medical record number, will be stored in a secure database for 3 years. Only the investigator and the designated members of the study team will have access to the separately-stored master list. All electronic records pertaining to the clinical study will be password-protected, and only approved study members listed on the IRB protocol will have password access. Any information about the subject collected on paper will be kept under lock and key in designated place at the corresponding participating site.

- 240 1. De Pastena M, Paiella S, Marchegiani G, et al. Postoperative infections represent a major determinant
- of outcome after pancreaticoduodenectomy: Results from a high-volume center. Surgery 2017;162:792-801.
- 242 2. Badia JM, Casey AL, Petrosillo N, et al. Impact of surgical site infection on healthcare costs and

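### Published blocks of two or four within centre-by-wound strata let unblinded investigators infer many allocations, so the concealment claim covers only the next list entry

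*Protocol*

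**What the plan says.** Protocol section 3.E (Randomization and blinding) sets three things.

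- Strata: "Stratification will be performed according to the participating center and the type of wound classification". The wound factor has two levels: "one group with clean or clean-contaminated wounds and the other group with contaminated or dirty, infected wounds".
- Blocks and blinding: "A permuted block randomization with the size of two or four will be applied. Participating investigators cannot be blinded to the allocated treatment". It does not say whether the sizes are mixed at random, in what proportion, or whether they are withheld from sites. Patients and the data manager are blinded.
- Concealment: allocation comes from a web registry "immediately before the beginning of the operation, providing adequate concealment for the allocation sequence".

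The executive summary gives the number of centres: "Up to 13 sites of secondary or tertiary hospitals in South Korea". Section 3.D places consent and registration before the trial intervention. Section 3.M allows the principal investigator, a surgeon co-investigator or a study coordinator to take consent.

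**The concern.** Concealment has two parts. The next assignment must be hidden, and it must not be deducible from assignments already seen. The web release deals with the first part. The second depends on block size, on how many lists there are, and on who sees past allocations. Here the blocks are the smallest possible, the lists are numerous and short, the sizes are printed in the protocol, and the people who may recruit can see which arm earlier patients received.

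Someone who expects a particular arm next could defer a patient or not approach that patient. Baseline risk matters here: section 3.L(1) assumes SSI rates of about 10%, 25% and 40% for clean/clean-contaminated, contaminated and dirty wounds. The last two classes share one stratum, so stratification does not prevent selection between them. The wound group is also needed before allocation, and no step is described that fixes it irrevocably first.

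**Working it through.** **The plan's own figures.** The protocol states no predictability figure. Its sample size enters only through list length, and it reproduces. Control rate: 0.2×10% + 0.4×25% + 0.4×40% = 28%. A 40% reduction gives 16.8%. At two-sided 5% and 80% power this needs 217 per arm, or 434. Then 217/0.95 rounds up to 229 per arm, or 458. The planned difference is 28 − 16.8 = 11.2 points.

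**List length.** 13 centres × 2 wound groups = 26 lists, and 458/26 = 17.6, so about 18 on average. The lists will be unequal. With 13 equal centres and the assumed 20:80 split, they would hold 458×0.2/13 = 7 and 458×0.8/13 = 28 patients.

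**Single block size, all earlier allocations on the list seen.**
- Size 2: the second of each pair is certain, so 1/2 = 50%. Best guess right: (0.5 + 1)/2 = 75%.
- Size 4: with probability 1/3 the first two match and the last two are certain; otherwise only the fourth is. Expected certain per block: 1/3×2 + 2/3×1 = 1.33, or 33% over complete blocks. A list of 18 has four full blocks and two further patients: 4×1.33/18 = 30%. Best guess right: 69%.

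**Equal random mix of 2 and 4 (assumed), block boundaries not known.**
- Certain: only when one arm is two ahead, which reveals a block of four and fixes its last two places. Per block this has probability 0.5×1/3 = 1/6 and yields two certain allocations, so 1/3 per block of mean length 3, or 11% in the long run.
- One arm behind: 1 place in a block of two, and 1/3×3 + 2/3×2 = 2.33 places in a block of four. (1 + 2.33)/6 = 56% in the long run. In the simulation about 55% of allocations were predictable with at least 75% probability.
- Guessing the arm that is behind: (1.5 + 2.83)/6 = 72% right.

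**Simulation** (4,000 lists per scheme, length 18, exact updating over block size and position):

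| Scheme | Certain | Probability ≥ 75% | Best guess right |
|---|---|---|---|
| 2 only | 50% | 50% | 75% |
| 4 only | 30% | 30% | 69% |
| 2/4 equal mix | 10% | 55% | 72% |
| 4/6/8 equal mix | 2% | 37% | 67% |

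Chance alone is 50% right. For the 2/4 mix, lists of 6 and of 40 give 8% and 11% certain, and 71% and 72% right, so unequal lists change little.

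**What this could do to the estimate (illustration only).** Suppose patients enrolled when the device is expected differ in SSI risk by δ from those enrolled when gauze is expected. The bias is then about (2×0.72 − 1)×δ = 0.44δ: 2.2 points for δ = 5 and 4.4 points for δ = 10, against 11.2 planned. The documents give no value for δ. Through wound class alone, within the contaminated/dirty stratum, δ = 5 would need the share of dirty wounds to differ by 5/(40 − 25) = one third between the two situations. That is a large shift.

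**The case against.** Several safeguards narrow the opening. Consent and registration precede allocation, which is released only at surgery. All gastrointestinal patients having open surgery are to be screened, and registered patients who prove ineligible are logged with reasons. Emergent cases leave little room to defer. Several surgeons may share a list, and every figure above assumes one observer who follows all of it. The main analysis is by intention to treat. All of this stands, and it lowers the exposure. None of it prevents a decision before consent by someone who has seen the earlier allocations.

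Four stronger readings are tempting, and the documents do not support them.

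- A reader might compute that 39% of allocations are fully determined under a 2/4 mix, (1 + 1.33)/6, against 25% under 4/6/8. That requires knowing where each block starts and its length. An observer who knows only the possible sizes is certain for about 10% against 2%.
- A reader might infer that the primary comparison is biased. The documents show an opportunity, not an occurrence.
- A reader might infer that the surgeon chooses the stratum. The protocol does not say who enters the wound group; section 3.J lets an investigator or a research coordinator enter eCRF data.
- A reader might expect that hiding or enlarging the blocks cures the problem. Guessing the arm that is behind needs no knowledge of the sizes, and larger blocks lower the success rate only from 72% to 67%.

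**Conclusion.** The point holds as a design weakness of moderate size. The claim of "providing adequate concealment for the allocation sequence" is right for the entry about to be released and too broad for what earlier entries reveal. The share of certain allocations runs from about 10% (equal random mix) to 30% or 50% (a single size of 4 or 2). The protocol does not settle which case applies. In the mixed case more than half of allocations are still predictable with at least 75% probability. These figures rest on an observer who follows a complete list, lists of about 18, and, for the mix, equal proportions. Whether anyone acted on such predictions cannot be told from the documents, and the bias figures depend wholly on an assumed δ.

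**What to change.** **If allocations remain:** drop size 2 and use randomly varied blocks of 4, 6 and 8. Keep the sizes in a restricted randomisation document rather than in the protocol that sites hold. Have the web system lock eligibility and wound group before the allocation is shown. This costs a new list from the biostatistician and a locked field, and the maximum within-stratum imbalance rises from 2 to 4. The main gain is fewer certain allocations (about 10% to 2% for the mixed scheme); the gain in guess rate is modest.

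**If recruitment is complete:** the missing-values text under Final Statistical Analysis Plan reports observed percentages in the past tense, which suggests this case. Then:

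- report the block sizes actually used and how they were mixed;
- compare baseline risk by predicted allocation or position in block;
- compare the wound group used for stratification with the CDC class recorded under section 3.J;
- reword the concealment statement so that it claims only that the upcoming assignment was hidden until release.

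These checks use data the protocol already collects, plus the randomisation list, and cost some analyst time.
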